#### 10.3 VITAL SIGNS

Descriptive statistics for vital sign values and their changes from baseline at each visit will be presented by treatment group for the following vital sign parameters:

- Heart rate
- Respiratory rate
- Temperature
- Blood pressure (seated)
- Weight

Vital sign values will be classified as "normal", "low", or "high" based on standard criteria listed in Table 6 below. Shift tables for each parameter will be tabulated by treatment group.

Vital Sign Criteria Observed Value Parameter High Heart Rate  $\ge 100$ (beats per minute) Low ≤ 60 High  $\geq 20$ Respiratory Rate (breaths per minute) Low ≤ 12  $\ge 140$ High Systolic Blood Pressure (mm Hg) Low ≤ 85  $\geq 90$ High Diastolic Blood Pressure (mm Hg) Low  $\leq 50$ 

**Table 6: Standard Criteria for Vital Signs** 

## 10.4 ASSESSMENT OF TUMOR PROGRESSION

Scans at 12 weeks and 12-months post-RT will be compared to the initial images using the RECIST 1.1 system as outlined in Tables 3, 4, and 5 and compared for overall classification as well as the target and non-target lesion evaluations. The number and percentage of patients in each overall response category will be summarized by treatment group.

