In the mITT population, the number of patients with RECIST evaluations categorized as complete responses to therapy was increased from 15/38 (39%) in the placebo group to 17/36 (47%) in the 1.5 mg/kg SGX942 dose group, a 21% increase. Disregarding those patients with missing or not assessed tumor status, this increase was 34% in the SGX942 1.5 mg/kg group. This is consistent with preclinical studies showing improved survival and decreased tumor volume size (3). Over the longer term, the overall resolution rate in the placebo population was high, making further improvement difficult to demonstrate. However, SGX942 definitely did not decrease the effectiveness of CRT therapy (Table 4). Similarly, the overall 1-year survival rate was similar between groups and more favorable for the SGX942 treated groups (Table 5).

Table 4: Incidence of Tumor Complete Response as a Function of Treatment Group and Timepoint (Safety Population)*

RECIST Response	Placebo n = 41	1.5 mg/kg n = 42	3.0 mg/kg n = 3	6.0 mg/kg n = 23
1-month follow-up	15/32 (47%)	17/27 (63%)	1/3 (33%)	4/16 (25%)
3-month follow-up	17/27 (63%)	18/27 (67%)	1/1 (100%)	9/17 (53%)
6-month follow-up	19/24 (79%)	19/28 (68%)	1/1 (100%)	10/14 (71%)
9-month follow-up	6/8 (75%)	14/16 (88%)	2/2/ (100%)	1/3 (33%)
12-month follow-up	22/23 (96%)	19/23 (83%)	1/2 (50%)	10/12 (83%)
LOCF** through 12-month follow-up	26/35 (74%)	28/35 (80%)	1/3 (33%)	13/22 (59%)

^{*}Percentage calculation excludes missing/not assessed evaluations

Table 5: Mortality (ITT Population¹)

Mortality	Placebo	1.5 mg/kg	3.0 mg/kg	6.0 mg/kg
	n = 43	n = 41	n = 3	n = 24
Through 12-month follow-up	9 (21%)	3 (7%)	0	4 (17%)

¹ Includes one patient dying 373 days after receiving their last study drug dose

[figure not shown]
Original: 11 January 2017 Amendment 1: 29 November 2017 Amendment 2: 22 January 2018 Amendment 3: 17 September 2019

^{**} Last Observation Carried Forward

The survival curves for the 1.5 mg/kg SGX942 and placebo groups are shown in Figure 5.

Figure 5: Survival Curve

[figure not shown]

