In this Phase 2 trial, confidence in the benefit of SGX942 is based not only on the magnitude of reduction in the duration of SOM and the concordance of the patient results with both qualitative and quantitative animal model data, but also in the internal consistency of the trial data. The duration data, AUC data, and incidence data consistently trend in the same direction and are similar across analysis populations (i.e., per protocol [PP], mITT, and ITT populations) as well as across subpopulations of groups defined by baseline characteristics (i.e., cisplatin treatment, HPV tumor status, age, sex, race, and prior tumor surgery). The additional findings of an increase in the number of patients with RECIST defined "complete response" and a reduction in the number of infections in the SGX942 dose groups are consistent with the animal model studies and strongly support the evidence for biologic activity of the drug in this patient population.

With its rapid degradation yet extended PD impact, the PK profile of SGX942 is of limited utility. Nonetheless, evaluating PK in a subset of patients demonstrated a roughly or greater than dose proportional response in C_{max} and area under the concentration time curve (AUC) of SGX942 in blood in response to increased dose levels (i.e., 1.5 vs. 6.0 mg/kg). There was no evidence of accumulation over multiple doses. These results were consistent with the nonclinical and Phase 1 clinical PK results.

Comparison of the AEs and SAEs across the dose groups (i.e., 1.5, 3.0, and 6.0 mg/kg) did not reveal any substantive differences in the incidence, severity, PI judgments as to relatedness or severity of the AEs, or specific AEs. The infusion procedures themselves were well tolerated. Complete resolution of tumor burden was similar or improved in the SGX942 1.5 mg/kg treatment group and all-cause mortality was also similar across treatment groups, with the best outcome in the 1.5 mg/kg SGX942 treatment group. SGX942 administration at all dose levels appeared to be safe and well tolerated.

[figure not shown]

Confidential

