11.1.4 Assessment of Tumor Progression at 12 weeks and 12-months Post-RT

Scans at 12 weeks and 12-months post-RT will be compared to the initial images using the RECIST 1.1 system as outlined in Table 9, Table 10, and Table 11. The percent of the patients categorized as having a "complete tumor response" at 12 weeks and 12 months post-RT will be compared between the treatment groups. Additionally, the percent of the patients categorized as having a "complete tumor response" or "partial tumor response" at 12 weeks and 12 months post-RT will be compared between the treatment groups.

11.1.5 **Infections**

Patients will be assessed at each clinical visit through the 6-week post-RT visit as to the presence of probable clinical infections. All clinical diagnoses of infections will be classified as presumed fungal, presumed viral, or presumed bacterial. The severity of each infection will be graded using the CTCAE (Appendix 1). The incidence of all reported infections, the number of patients with reported infections, the number of presumed fungal, the number of presumed viral and the number of presumed bacterial infections will be compared between treatment groups. The incidence of each type of infection (fungal, viral, and bacterial) by severity grade (1-5) will be displayed.

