12. STATISTICS

12.1. Overview

Complete details of analyses and relative order of importance of each analysis are more fully delineated in the Statistical Analysis Plan.

Given the anticipated non-Gaussian distribution of values for duration of OM, the severity-weighted OM calculations (AUC), and the days to onset of OM, treatment groups will be compared for these variables using a log-rank test of the differences in the duration of SOM between the SGX942 and placebo treated groups. The incidence of OM, percent of RECIST complete responders, and percent of patients with each category of infection will be compared using chi-squared tests. The primary analysis population will be patients who have received enough radiation exposure to put them at significant risk of developing SOM (defined as a cumulative radiation dose of at least 55 Gy).

Original: 11 January 2017 Amendment 1: 29 November 2017

Amendment 2: 22 January 2018 Amendment 3: 17 September 2019

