### 2.3 SAFETY ENDPOINTS

- Comparison of the incidence, type, and body system categorization of AEs
- Comparison of the incidence, type, and body system categorization of SAEs
- Comparison of the changes from Baseline for hematology parameters, clinical chemistry parameters, and vital signs
- Comparison of tumor status at 12 weeks and 12 months following completion of RT categorized using the RECIST [1.1] criteria
- Comparison of the incidence and severity of reported infections assessed by CTCAE grading
- Comparison of all-cause mortality through 12 months follow-up
- Comparison of progression-free survival through 12 months follow-up

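### SAP 10.4 only tabulates tumour response, although the protocol promises a between-arm comparison, and neither document says how deaths and missing scans are counted

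*SAP*

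**What the plan says.** RECIST status at 12 weeks and 12 months is a named safety objective (Protocol 5.3, SAP 1.3). The documents treat its analysis as follows.

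- **Protocol 11.1.4:** the percentage with CR, and separately the percentage with CR or PR, "at 12 weeks and 12 months post-RT will be compared between the treatment groups".
- **Protocol 12.1:** "The incidence of OM, percent of RECIST complete responders, and percent of patients with each category of infection will be compared using chi-squared tests". The synopsis also names chi-squared for CR. No test is named for CR+PR.
- **SAP 2.3** lists as a safety endpoint "Comparison of tumor status at 12 weeks and 12 months following completion of RT".
- **SAP 10.4**, the section that should give the method: "The number and percentage of patients in each overall response category will be summarized by treatment group". Its own use of the word compared refers to follow-up scans against the initial images.
- **SAP 10.6 and 10.7** do name tests: chi-square and log-rank for deaths, log-rank for progression-free survival (PFS).

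Neither document says how a death, a recurrence or an absent scan enters the response percentage. The only precedent is the footnote to the Phase 2 response table (Protocol 4.5, Table 4): "Percentage calculation excludes missing/not assessed evaluations". From that table the protocol concludes: "Complete resolution of tumor burden was similar or improved in the SGX942 1.5 mg/kg treatment group".

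**The concern.** A drug given alongside curative chemoradiation needs a direct check that it does not also protect the tumour, and the two scheduled scans are that check. A statistician following SAP 10.4 as written would produce a frequency table and stop, so a safety comparison promised in the protocol would not be made.

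The missing denominator rule is the second problem. If many patients have no 12-month scan, the CR percentage depends heavily on who is left in the denominator. If that choice is open when the data are unblinded, the sign of the difference can depend on it.

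**Working it through.** **1. The two documents side by side**

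| Element | Protocol 11.1.4, 12.1, synopsis | SAP 10.4 |
|---|---|---|
| CR between arms | Compared, chi-squared | Percentage by arm only |
| CR+PR between arms | Compared | Not formed |
| Confidence interval for the difference | None | None |
| Death, recurrence or missing scan | No rule | No rule |

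The first two rows are conflicts. The last two are gaps in both documents.

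**2. Reproducing the Phase 2 figures**

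Inputs are from Protocol 4.5, Table 4 (Safety set, 41 placebo and 42 on 1.5 mg/kg). At 12 months, placebo 22/23 = 95.7% and 1.5 mg/kg 19/23 = 82.6%, matching the printed 96% and 83%. Unassessed: (41 - 23)/41 = 44% and (42 - 23)/42 = 45%.

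**3. Does the denominator change the answer?**

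The difference is 1.5 mg/kg minus placebo. The interval is Newcombe's: with Wilson limits (l, u) for each proportion and D = p1 - p2, lower = D - sqrt[(p1 - l1)² + (u2 - p2)²] and upper = D + sqrt[(u1 - p1)² + (p2 - l2)²].

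Scanned patients only: p1 = 82.6% (62.9 to 93.0), p2 = 95.7% (79.0 to 99.2). Then D = -13.0, lower = -13.0 - sqrt(19.7² + 3.5²) = -33.1, upper = -13.0 + sqrt(10.4² + 16.7²) = +6.6 (limits computed before rounding).

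| Handling at 12 months | 1.5 mg/kg | Placebo | Difference, points (95% CI) |
|---|---|---|---|
| Scanned only | 19/23 | 22/23 | -13.0 (-33.1 to +6.6) |
| All unassessed counted as non-CR | 19/42 | 22/41 | -8.4 (-28.4 to +12.6) |
| Deaths added as non-CR (approximate) | 19/26 | 22/32 | +4.3 (-19.0 to +26.1) |
| Last observation carried forward (Table 4) | 28/35 | 26/35 | +5.7 (-13.9 to +24.9) |

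The third row adds the Table 5 deaths (3 and 9) to the scanned patients: 23 + 3 = 26 and 23 + 9 = 32. It is approximate. It assumes no patient who died had a 12-month scan, and it mixes Table 5's ITT set (41 on 1.5 mg/kg, 43 placebo) with Table 4's Safety set. Table 5's footnote also says that one counted death came 373 days after the last dose, so that patient could have been scanned.

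**4. The other time points (scanned patients)**

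| Month | 1.5 mg/kg | Placebo | Difference, points (95% CI) |
|---|---|---|---|
| 1 | 17/27 | 15/32 | +16.1 (-9.0 to +38.4) |
| 3 | 18/27 | 17/27 | +3.7 (-20.7 to +27.5) |
| 6 | 19/28 | 19/24 | -11.3 (-33.2 to +12.9) |
| 9 | 14/16 | 6/8 | +12.5 (-17.0 to +47.7) |

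The sign changes over time and every interval includes zero. Two-sided Fisher p is 0.53 at 6 months and 0.35 at 12 months.

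**5. What Phase 3 could deliver**

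The documents give no expected CR rate for Phase 3, so I take 63% to 96%, the placebo rates at 3 and 12 months in Table 4. With equal rates p in both arms and n scanned per arm, half-width = 1.96 × sqrt[2p(1 - p)/n].

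- n = 130 (all planned patients scanned): 1.96 × sqrt(2 × 0.96 × 0.04/130) = 4.8 points; with p = 0.63, 11.7 points.
- n = 72 (about 130 × 0.55, missingness as in Phase 2): 6.4 and 15.8 points.

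**The case against.** The strongest counter-argument is that tumour safety is already tested elsewhere. SAP 10.6 compares deaths by chi-square and log-rank. SAP 10.7 compares PFS by log-rank, with progression status collected monthly, death as an event and no need for a 12-month scan. This stands: it would be wrong to say that the plan leaves tumour safety unexamined. It does not replace the response comparison, however. SAP 10.7 counts a new or recurrent cancer or further chemotherapy as progression, whereas Protocol 11.1.7 also counts imaging that shows less than complete response. Under the SAP, residual disease on a scan without one of its own events is not progression. SAP 10.4 is therefore the main place where the scan result itself is analysed.

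Second, the comparison is in the protocol and in the SAP's endpoint list, and table specifications sit in separate shells that I have not seen. This limits the defect to a missing method and denominator in the SAP. A shell could specify a denominator, but the test and the rule belong in the SAP.

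Third, counting a death as non-response mixes mortality with tumour response. This is a fair reason to debate which rule should be the main one, but not to leave the rule unstated.

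A reader might also infer from the 6- and 12-month rows of Table 4 that 1.5 mg/kg impaired tumour control. The documents do not support that. The 1-, 3- and 9-month figures and the carried-forward figure favour 1.5 mg/kg, and no difference is distinguishable from chance. Protocol 4.5's opposite claim, that SGX942 definitely caused no loss of chemoradiation effectiveness, is also stronger than intervals reaching about -33 points allow.

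**Conclusion.** The point holds as a conflict between protocol and SAP on a named safety objective. If SAP 10.4 is followed as written, the promised comparisons of CR and CR+PR are dropped, and neither document fixes the denominator. PFS and mortality testing reduces what is at stake but leaves the RECIST objective without inference.

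The Phase 2 data show why the denominator rule matters: the same 12-month follow-up gives differences from -13.0 to +5.7 points, depending on how unassessed patients are handled. The deaths-as-non-CR figure of about +4 is only approximate, and the change of sign does not rest on it, because the carried-forward figure is also positive. The width of these intervals describes Phase 2 and is not the size of the Phase 3 defect. In Phase 3 what is lost is an interval with a half-width of about 5-12 points if all 130 per arm are scanned, or 6-16 points with missingness like that of Phase 2, under the assumed CR range of 96% to 63%.

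Restoring the chi-squared test alone would not be enough. Neither document sets a margin, and a non-significant difference would not show absence of harm, so the interval is the useful output.

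**What to change.** In SAP 10.4:

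1. Restore the protocol's comparison of CR and of CR+PR at 12 weeks and 12 months, with the chi-squared test the protocol names for CR.
2. For each, report the difference SGX942 minus placebo with a two-sided 95% CI.
3. Before unblinding, fix one main denominator in the Safety population. State how each of these is counted: death before the scan, recurrence before the scan, and a missing scan in a living, recurrence-free patient.
4. Show scanned-only and missing-as-non-response results as sensitivity rows.

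The cost is a paragraph of SAP text and one more table. Scans, vital status and recurrence are already collected (Protocol 6.3.10 to 6.3.12). The downside is that CR rates will probably look lower than scanned-only rates. Softening the Phase 2 sentence in Protocol 4.5 is an optional background edit that changes no Phase 3 analysis.

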#### 10.5 INFECTIONS

Patients will be assessed at each clinical visit through the 6-week post-RT visit as to the presence of probable clinical infections. All clinical diagnoses of infections will be classified as presumed fungal, presumed viral, or presumed bacterial. The severity of each infection will be graded using the CTCAE (see protocol appendix 1).

The number and percentage of patients with any reported infections, presumed fungal infections, presumed viral infections and presumed bacterial infections will be summarized by treatment group. The incidence of patients with all reported infections and each type of infection (fungal, viral, bacterial) by severity grade (1-5) will be displayed.

#### 10.6 ASSESSMENT OF MORTALITY

All deaths through the 12-month follow-up visit will be collected. The number of deaths in each treatment group will be compared using a standard chi-square analysis. Time to death and the cumulative probability of death will be summarized using Kaplan-Meier estimates. In addition, a log-rank test will be used to compare the survival distributions between treatment groups. Kaplan-Meier survival curves will be plotted for both treatment groups.

#### 10.7 PROGRESSION-FREE SURVIVAL

The date that a patient's cancer progress, defined by a diagnosed with a new cancer, recurrent cancer or initiates more chemotherapy, will be collected on a monthly basis. Progression-free survival will be calculated from the time of enrollment to the earliest of date of cancer progression, death, or 12 months. If a subject drops out, withdraws or is terminates participation study early for some other reason, the subject will be censored at the last know status. Kaplan-Meier progression free survival curves with be constructed for the treatment groups and the curves compared using a log-rank test.

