6.3.10 Monthly (2- to 11-Month Post-RT) Follow-up Contacts

All patients will be contacted at least once per month (±2 weeks) through 11 months (except for the 12 week/3 month follow-up visit) following completion of their last RT treatment through

Original: 11 January 2017 Confidential Page 39 of 67

either clinic visits or telephone contacts. For each contact, the following information that will be entered into the eCRF:

- Vital status
- Evidence of recurrence of the primary tumor
- Initiation of additional anti-cancer therapy

6.3.11 12 weeks (3-Month) Post-RT Follow-up Visit

Patients will have a clinic visit at 12 weeks (± 3 weeks) and the following will be performed:

- Interim Medical History
- History of pain and opioid use
- Repeat of the same scans used at the initial tumor staging to be used in a RECIST 1.1 comparison
- Record of tumor status including evidence of tumor recurrence and additional anti-cancer therapies

6.3.12 **12 Month Post-RT Follow-up Visit**

Patients have their last study visit at 12 months (± 28 days) post-RT and the following will be performed:

- Interim Medical History
- History of pain and opioid use
- Evaluation of tumor status
- Repeat of the same scans used at the initial tumor staging to be used in a RECIST 1.1 comparison

Amendment 2: 22 January 2018 Amendment 3: 17 September 2019

Page 41 of 67

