11.1.6 Assessment of Mortality Through the 12-month Post-RT Clinic Visit

All deaths through the 12-month follow-up visit will be collected. The number of deaths in each group will be compared using a standard chi-squared analysis. The number of deaths over time will be compared using a Kaplan-Meier survival curve and the survival curves compared using a log-rank test.

11.1.7 **Progression-free Survival**

The duration of progression free survival will be calculated from the date of randomization to the earliest date of the following:

Original: 11 January 2017

Page 53 of 67

- The patient died
- The patient had an imaging report of tumor progression (RECIST 1.1 evaluation of less than "Complete Response")
- The patient completed their 12 month follow-up assessment.

Patients lost-to-follow-up will be censored at the time of their last assessment.

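### Read literally, SAP 10.7 stops progression-free survival 12 months after enrolment, before the 12-month post-RT scan of any patient who completes planned radiotherapy, in conflict with Protocol 11.1.7

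*SAP*

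**What the plan says.** Two texts define how long PFS is observed.

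- SAP 10.7: "Progression-free survival will be calculated from the time of enrollment to the earliest of date of cancer progression, death, or 12 months". It counts as progression a new cancer, a recurrence or further chemotherapy, collected monthly, and censors early leavers at last known status.
- Protocol 11.1.7: "The duration of progression free survival will be calculated from the date of randomization to the earliest date of the following". The list that follows is death, an imaging report of progression, or the point at which "The patient completed their 12 month follow-up assessment".

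The 12-month assessment is anchored to radiotherapy. Protocol 6.3.12 says "Patients have their last study visit at 12 months (± 28 days) post-RT", and the schedule of events in both documents puts it at study week 59, counting post-RT time from the last radiation treatment. After screening, the only scheduled tumour scans are at 12 weeks and 12 months post-RT.

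Two other SAP sections bear on the horizon. SAP 2.3 lists the endpoint as "Comparison of progression-free survival through 12 months follow-up", and SAP 10.6 says of mortality that "All deaths through the 12-month follow-up visit will be collected".

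**The concern.** PFS is one of the analyses meant to show that a drug given alongside chemoradiation does not impair tumour control. SAP 10.7 is the only SAP text that says how to calculate it. A programmer who follows it as written would count 12 months from enrolment.

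The trial's 12-month visit comes 12 months after radiation ends, which is weeks later. The last scan would then fall outside PFS. A recurrence first found on that scan would be dated after the cut-off and would not count. A death in week 55 would be an event in the SAP 10.6 mortality analysis but not in PFS, for the same patient in the same Safety Population. The PFS result would also differ from the one the protocol describes.

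**Working it through.** **Reproducing the plan's own figure.** The schedule assumes 7 weeks of radiation. 7 + 12 = week 19 for the first scan and 7 + 52 = week 59 for the second. Both match the schedules. Twelve months from enrolment is 365.25 / 7 = week 52.2, so the nominal second scan is about 7 weeks past a literal cut-off.

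**Inputs for the range**
- Planned dose 55 to 72 Gy in single daily fractions of 2.0 to 2.2 Gy (Protocol 7.1, criterion 5).
- Five fractions a week (schedule of events).
- Visit window of ±28 days (Protocol 6.3.12).
- Randomization at Baseline, before radiation starts (Protocol 6.3.2).

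**Formula.** Let L be the day of the last fraction, counted from the first, and e the number of days by which enrolment precedes the first fraction. Counted from the first fraction, the literal cut-off is day 365 − e, the nominal scan is day L + 365, and the earliest in-window scan is day L + 337. So:
- nominal overshoot = L + e
- overshoot of the earliest in-window scan = L + e − 28

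The table takes a Monday start, no breaks and e = 0.

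| Planned course | Fractions | L | Nominal scan | Earliest scan | Earliest minus day 365 |
|---|---|---|---|---|---|
| 55 Gy at 2.2 Gy | 25 | 32 | day 397 | day 369 | 4 days |
| 66 Gy at 2.2 Gy | 30 | 39 | day 404 | day 376 | 11 days |
| 70 Gy at 2.0 Gy | 35 | 46 | day 411 | day 383 | 18 days |
| 72 Gy at 2.0 Gy | 36 | 49 | day 414 | day 386 | 21 days |

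The 7-week course gives day 411 here and 59 × 7 = 413 by week count, because the last fraction falls on a Friday rather than at the end of the week.

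**Follow-up lost on the literal reading.** 397 − 365 = 32 days to 414 − 365 = 49 days. As a share of follow-up from the start of radiation, that is 32/397 = 8% to 49/414 = 12%. On the 7-week calendar the 11-month contact (about week 55) also falls outside. The 10-month contact (about week 50) and the week-19 scan fall inside.

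**Exception.** An in-window scan can precede the cut-off only if L + e ≤ 28. That means radiation ending by day 28 if e = 0, or by day 24 if e = 4. Such patients have had at most 21 fractions, or 21 × 2.2 = 46.2 Gy. They are outside the mITT population but can be in the Safety Population, where PFS is analysed (SAP 10), because it has no minimum radiation dose.

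**Event definition.** SAP 10.7 uses clinical events, "defined by a diagnosed with a new cancer, recurrent cancer or initiates more chemotherapy, will be collected on a monthly basis". Protocol 11.1.7 uses an imaging report, with any RECIST result short of complete response counting. Aligning the horizon alone would not make the two PFS definitions agree. Both texts also list the end of observation among the dates that stop the clock, without saying that it is a censoring time.

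**The case against.** The best defence is that SAP 10.7 does not say 12 months after enrolment. Enrolment sets the origin, and the bare 12 months could mean the follow-up visit. SAP 2.3 supports this by giving mortality and PFS the same horizon in the same words. SAP 2.4.2 has recurrence data collected to 12 months after the last radiation treatment, and the SAP describes itself as an elaboration of the protocol. This stands as far as it goes: the enrolment-anchored cut-off is the literal reading, not the only one. It does not remove the problem. An endpoint label does not override the calculation rule, and if the label is right, SAP 10.7 contradicts its own endpoint list as well as the protocol.

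A reader might go further and infer three things that the documents do not support.

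- *That the 12-month scan can never count.* Patients who stop radiation within about four weeks are an exception, and Protocol 6.1 expects some to stop early.
- *That a late excess of deaths or progression would go unseen in the trial.* SAP 10.6 analyses all deaths to the 12-month visit by chi-square, Kaplan-Meier and log-rank. SAP 10.4 tabulates 12-month RECIST categories by arm. Recurrence found earlier still counts in PFS.
- *That the cut-off biases the comparison.* A fixed limit from enrolment applies equally to both arms. The fault is the conflict with the protocol and with the mortality horizon.

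**Conclusion.** Wrong as written, for a safety endpoint only; the primary analysis and sample size are unaffected. Followed literally, SAP 10.7 gives a PFS that ends 32 to 49 days before the nominal assessment at which Protocol 11.1.7 ends it. It leaves out the second of two post-baseline scans for every patient who completes a planned course, even at the early edge of the visit window. The margin at that edge is thin for the shortest course (4 days) and wider for the 7-week course that the schedule assumes (18 days).

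The calculation assumes five fractions a week, a Monday start, no breaks and enrolment on the first day of radiation. Breaks, other start days or earlier enrolment only move the scan further past the cut-off. The documents give no progression rate for the period concerned, so the number of PFS events at stake cannot be calculated from them.

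**What to change.** Replace the calculation sentence in SAP 10.7 with wording such as:

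> PFS is measured from the date of randomization to the earlier of progression or death. Patients with neither are censored at the 12-month post-RT follow-up assessment, or at last known status if they leave earlier.

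This matches Protocol 11.1.7 and the horizons in SAP 2.3 and 10.6. It also makes clear that reaching the assessment is censoring and not an event. In the same edit, settle one definition of progression for both documents and say how a finding on the 12-month scan is dated.

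The cost is a short SAP revision. No new data are needed, because the scans, contacts and death reports are already scheduled. It must be in place before the second, long-term analysis in Protocol 12.3, and preferably before the first, since that section promises continued blinding only for site personnel.
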